#### ***9.1.1.2 Primary Analysis of the Primary Estimand***

The primary analysis of time to hospital discharge will be a Cox proportional hazards model with time to hospital discharge calculated according to [Section 5.3.1.1](#).

Covariates will be included in the proportional hazards model as per [Section 7.2](#).

The hazard ratio for hospital discharge of SNG001 versus placebo, 95% confidence intervals (CI) and p-value will be presented. In addition, unadjusted quartile estimates will be calculated through the Kaplan-Meier method with 95% CI calculated by the Brookmeyer-Crowley method.

Ties in event times will be handled using the exact method, or the Efron approximation if computational difficulties arise. Schoenfeld residuals will be plotted to assess the proportional hazards assumption.

The Restricted Mean Survival Time (RMST) will also be presented.

The statistical significance of the primary analysis of time to hospital discharge will be formally assessed by the Hochberg procedure, as detailed in [Section 7.6](#), and a statistically significant p-value according to the multiple testing strategy will be indicated in the output.

The hazard ratios for hospital discharge and for recovery in SNG001 versus placebo and their corresponding 95% CI and p-values will be presented in a forest plot, in which the x-axis will represent the hazard ratio and the y-axis will stand for the estimates of the two co-primary endpoints.

The proportion (%) of patients who were discharged from hospital on or before visit up to Day 28 will be presented in a table alongside the probability of survival calculated from a Kaplan-Meier analysis and Greenwood 95% confidence intervals. Plots will be produced of Kaplan-Meier estimates over time and the proportion (%) of patients who were discharged from hospital on or before visit up to Day 28 for SNG001 versus placebo.

#### ***9.1.1.3 Sensitivity Analyses of the Primary Estimand***

The sensitivity of the primary analysis to missing data due to withdrawal from study prior to hospital discharge/ recovery will be assessed through a tipping point analysis, where missing data will be imputed

## Statistical Analysis Plan (RotW)

Final v1.0, 08FEB2022

SG018

as described by Jackson et al [6]. To perform the multiple imputation M datasets will first be created through bootstrapping. The bootstrapping will be applied independently for each treatment group (a treatment stratified bootstrap). Each created dataset will therefore contain  $n_1$  Placebo patients and  $n_2$  SNG001 patients where  $n_1$  and  $n_2$  are the number of patients randomised to Placebo and SNG001 respectively. The primary analysis method will be used to assess each of the bootstrapped datasets to generate estimates of the model coefficients within each dataset. The vector of model coefficients can be written algebraically for the  $j^{\text{th}}$  dataset as  $\beta_j^*$  and the vector of covariates values for the  $i^{\text{th}}$  patient as  $Z_i$ .

Missing hospital discharge and recovery times for patients censored prior to day 28 will be estimated as  $\min(T_{ij} = C_i + A_{ij}, 28)$ , where  $T_{ij}$  is the imputed time to discharge/recovery in the  $j^{\text{th}}$  dataset for the  $i^{\text{th}}$  patient,  $C_i$  is the observed censored time and  $A_{ij}$  is the simulated time between censoring and the time to event. A maximum constraint of 28 days is applied to the imputed times because the rate and time to hospital discharge and recovery beyond this time cannot be assessed due to the limitations of the study design.  $A_{ij}$  will be estimated using the Bender et al method [7], by the following calculation:

$$A_{ij} = H_{A_{ij}}^{-1}[-\log(U_{ij})\exp(-\beta_j^*Z_i - \gamma_i)],$$

where  $U_{ij}$  is randomly generated from a Uniform(0,1) distribution,  $H_{A_{ij}}^{-1}$  is the inverse cumulative baseline hazard function for  $A_{ij}$  and  $\gamma_i$  is a sensitivity parameter. If  $\gamma_i$  is set to 0 this will represent a Missing at Random (MAR) approach, if  $\gamma_i < 0$  the time to discharge/recovery will occur earlier than that of the MAR approach and if  $\gamma_i > 0$  discharge/recovery will occur later than that of the MAR approach. Values of  $\gamma$  will be varied independently for each treatment group.

The M imputed datasets will be analysed using the primary analysis model and the M estimates will be combined with Rubin's variance formula.

The value of M will be chosen large enough such that the choice of the seed used in sampling functions has a negligible impact on estimates.

For each imputed dataset and for each value of  $\gamma_i$  the primary analysis method will be repeated. The estimates from the imputed datasets will be combined for each value of  $\gamma_i$  using Rubin's rules [8]. The results for the different combinations of  $\gamma_i$  for Placebo and SNG001 patients will be plotted on a heat map to identify, if applicable, where the p-values becomes non-significant. This 'tipping point' will also be tabulated along with specific values of  $\gamma_i$  on the exponentiated scale.

A jump to reference Missing Not at Random (MNAR) data imputation will also be performed using similar a method, but only assuming all patients who withdraw early follow the same pattern as patients who are randomised to placebo.  $\gamma_i$  will be set to 0 for this imputation.

These sensitivity analyses will assess the robustness of the results to a departure from the censored at random assumption of a Cox proportional hazards model. To aid interpretation the average proportion of patients who were discharged from hospital will be presented alongside the average difference in the restricted mean survival time.

An additional sensitivity analysis will assess hospital discharge that has been sustained for 7 days. In this analysis patients will be considered as discharged from hospital if they are not re-admitted to hospital within 7 days of hospital discharge. This analysis will evaluate the the primary endpoint using the same rebound assessment period for all patients .

The primary estimand will be further evaluated for each of the subgroups described in [Section 7.2](#). The analysis method for the primary endpoint described in [Section 9.1.1.2](#) will be used to evaluate each subgroup.

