**Table 8: Intercurrent events and policies for the primary estimand of time to hospital discharge**

Intercurrent event	Policy
Death	Composite variable: Patients who die on or prior to Day 28 will have time to hospital discharge right censored at 28 days (the maximum time to discharge).
Premature treatment discontinuation and missed doses	Treatment policy: The time to hospital discharge will be used regardless of treatment discontinuation and the number of missed doses.
Withdrawal from study following hospital discharge	Hypothetical: The time to hospital discharge will be used regardless of study withdrawal where discharge was sustained for 7 days. Otherwise, patients will be censored at the last date known to be hospitalised for patients who withdrew during the 7 day rebound period. This approach has been proposed because discontinuation during the rebound period is expected to be due to lack of interest/lack

	of motivation/lack of time to continue participating in the study rather than relapse.
Withdrawal from study prior to hospital discharge	While-on-study: Time to hospital discharge will be right censored at the time of withdrawal from the study or at 28 days, whichever occurs first. The evaluation period for this endpoint is 28 days, therefore estimating the time to hospital discharge after Day 28 would not be appropriate. Premature study withdrawal is expected to be independent to the treatment effect, therefore a censoring approach in this scenario is considered appropriate. However, this assumption will be tested by appropriate sensitivity analyses.
Other protocol deviations and concomitant medications affecting efficacy	Treatment policy: Time to hospital discharge will be used regardless of any concomitant medication use or protocol deviations.

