**9.1.2.3 Sensitivity Analyses of the Primary Estimand**

The sensitivity to missing data will be assessed in the same way as described for time to hospital discharge in [Section 9.1.1.3](#).

The primary estimand will be further evaluated for each of the subgroups described in [Section 7.2](#). The analysis method for time to hospital discharge described in [Section 9.1.1.2](#) will be used to evaluate each subgroup.

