#### **9.2.1.3 Sensitivity Analyses of the Key Secondary Estimand**

The sensitivity of the key secondary analysis to missing data due to withdrawal from study prior to progression to severe disease or death will be assessed firstly through a tipping point analysis for a range of sensitivity parameters,  $\delta_i$ , for each  $i^{\text{th}}$  patient.  $\delta_i$  represents the change to the odds of severe disease or death. If  $\delta_i$  is set to 1 this will represent a Missing at Random (MAR) approach, if  $\delta_i < 1$  the imputed OSCi score will be lower than that of the MAR approach and progression to severe disease will be less common. If  $\delta_i > 1$  the imputed OSCi score will be higher than that of the MAR approach and progression to severe disease will be more common. Values of  $\delta$  will be varied independently for each treatment group.

Missing data will be imputed in M datasets. OSCi will be considered a categorical variable and the imputation algorithm will use a monotone logistic regression method to impute missing OSCi scores. Each of the covariates used in the primary analysis, including treatment group, will be included as covariates in the logistic regression. Missing data will be imputed iteratively by day, starting at day 2. For each subsequent day, the OSCi scores at prior days will be included as covariates, including the OSCi scores imputed in earlier iterations. This will not include the OSCi score at day 1 because this will always be 4, by design. However, because there are 34 scheduled visit days to be imputed in this way it is likely as the imputation progresses that the imputation model will become over-parameterised. To avoid this issue and to account for the fact that the most recent days are most likely to be predictive, only the OSCi score at the previous two days will be used as continuous covariates. Any imputations of 8 (death) will be “carried forward” to all future missing days after each step and not imputed again.

For each imputed dataset and for each value of  $\delta_i$  the primary analysis method will be repeated. The estimates from the imputed datasets will be combined for each value of  $\delta_i$  using Rubin’s rules. The results for the different combinations of  $\delta_i$  for Placebo and SNG001 patients will be plotted on a heat map to identify, if applicable, where the p-values becomes insignificant. This ‘tipping point’ will also be tabulated along with specific values of  $\delta_i$ .

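### In the tipping-point analysis of both primary endpoints, the imputation formula and the sentence explaining γ point in opposite directions

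*SAP*

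**What the plan says.** SAP Section 9.1.1.3 tests whether the primary result survives departures from independent censoring of patients who withdraw before discharge or recovery. Each such patient is given an imputed residual time after the censoring time, by the formula "A_{ij} = H_{A_{ij}}^{-1}[-\log(U_{ij})\exp(-\beta_j^*Z_i - \gamma_i" (closing brackets follow in the SAP). In this formula U is uniform on (0,1), H⁻¹ is the inverse cumulative baseline hazard, β comes from the Cox model fitted to a bootstrap sample, and γ is the sensitivity parameter. Imputed event times are capped at 28 days.

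The SAP then explains γ. Zero represents missing at random (MAR). For γ < 0, "the time to discharge/recovery will occur earlier than that of the MAR approach". For γ > 0, "discharge/recovery will occur later than that of the MAR approach". γ is varied separately in each arm. The combinations "will be plotted on a heat map to identify, if applicable, where the p-values becomes non-significant", and the tipping point is tabulated with γ "on the exponentiated scale". Section 9.1.2.3 carries the method over to the second primary endpoint: "The sensitivity to missing data will be assessed in the same way as described for time to hospital discharge".

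**The concern.** The formula and its explanation cannot both be right. In the formula γ has the same sign as βZ, so it acts as an addition to the log hazard of discharge or recovery. A larger γ must then mean an earlier event. The text says that a larger γ means a later one.

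This analysis has one product: a map showing how far, and in which direction, the post-withdrawal assumption must move before significance is lost. Protocol Section 8.4.1 pre-specifies it for both primary endpoints, and the sample size allows for 25% dropout. If the program is written from the formula and the axes are labelled from the text, the corner adverse to SNG001 and the corner favourable to it change places. A grid covering both signs would still contain every scenario, but mislabelled. A one-sided grid chosen from the text would leave out the scenarios adverse to SNG001. The SAP does not state the grid.

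**Working it through.** **Direction, by algebra.** Take A = H⁻¹[−log(U)·exp(−βZ − γ)].

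- −log(U) is positive, exp(−γ) falls as γ rises, and H⁻¹ is non-decreasing. So A falls as γ rises.
- Equivalently, P(A > a) = P(−log U > H(a)·exp(βZ + γ)) = exp(−H(a)·exp(βZ + γ)). The hazard of discharge or recovery after withdrawal is multiplied by exp(γ).
- This holds for any baseline hazard, covariate coding or endpoint. The 28-day cap can produce ties but cannot reverse the order.

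**Direction, in numbers.** SAP Section 6 gives exponential placebo rates of log(100/30)/28 for discharge and log(100/70)/28 for recovery. With βZ = 0 the median residual time is log(2)/(rate × exp(γ)). At γ = 0 this returns the SAP's own placebo medians of 16.1 and 54.4 days, so only the direction statement fails.

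| γ | Discharge: median residual time (days) | Recovery: median residual time (days) | SAP text says |
|---|---|---|---|
| −0.5 | 26.6 | 89.7 | earlier than MAR |
| 0 | 16.1 | 54.4 | MAR |
| +0.5 | 9.8 | 33.0 | later than MAR |

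At γ = −1 and +1 the discharge medians are 16.1 × 2.72 = 43.8 and 16.1 / 2.72 = 5.9 days. For a patient withdrawn at Day 10 (an assumed time), the chance of imputed discharge before Day 28 is 1 − exp(−18 × rate × exp(γ)) = 0.375, 0.539 and 0.721 at γ = −0.5, 0 and +0.5. Weibull baselines with shape 0.5, 1 and 2 gave the same order in every draw. Changing the exponent to +γ reproduces the SAP's sentence.

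**What a reversal would do to the map.** The planned analysis was simulated with 500 trials per scenario and 305 patients per arm. Inputs were the placebo rates above, hazard ratios of 1.45 (discharge) and 1.7 (recovery) from Protocol Section 8.1 and the opening of SAP Section 6, and exponential withdrawal of 25% over 28 days. Imputation used a treatment-stratified bootstrap, a Cox model without covariates, a Breslow baseline hazard conditional on the censoring time, 25 imputations, censoring of imputed times beyond Day 28, and Rubin's rules. The γ values are illustrative; the documents give none. The Monte Carlo standard error of mean Z is 0.04 to 0.05. Z > 1.96 refers to one endpoint alone, before Hochberg. About 14% of patients withdrew undischarged and 20% unrecovered.

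| Endpoint | (placebo γ, SNG001 γ) in the formula | Hazard ratio | Mean Z | Z > 1.96 |
|---|---|---|---|---|
| Discharge | (+1, −1): truly adverse to SNG001 | 1.20 | 1.87 | 45% |
| Discharge | (−1, +1): adverse according to the text | 1.72 | 5.58 | 100% |
| Recovery | (+1, −1): truly adverse | 1.32 | 1.97 | 51% |
| Recovery | (−1, +1): adverse according to the text | 2.14 | 5.34 | 100% |

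With placebo held at γ = 0, mean Z for discharge is 2.34, 2.86, 3.79 and 4.79 at SNG001 γ = −2, −1, 0 and +1. Moving SNG001 alone does not remove significance on average.

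**Whether another section settles it.** It does not. Tabulating γ on the exponentiated scale does not say what the exponentiated value multiplies. SAP Section 15 does not mention the point. In the key secondary tipping point (Section 9.2.1.3) a parameter above 1 means that "the imputed OSCi score will be higher than that of the MAR approach and progression to severe disease will be more common", so there larger is worse. Under the formula in 9.1.1.3 larger is better, and a reader moving between the two could carry the wrong orientation across.

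**The case against.** The algebra is not in dispute; the argument is about weight. The analysis is supportive, the program is not in the documents, and no wrong result has been shown. If the program follows the text, only a printed sign is wrong. Protocol Section 8.4.1 speaks of varying each arm independently and to varying degrees, so nothing suggests a one-sided grid. On a two-sided grid an alert reader would see Z rise where the label says later. SAP Section 9.1.1.3 also promises the average proportion discharged, though it does not say for each γ. All of this stands and limits the severity.

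The simulated cells are also a choice. Shifts of +1 and −1 in opposite arms change the relative post-withdrawal hazard by exp(2) = 7.4. In a smaller run of 120 trials, opposed shifts of 0.5 gave mean Z 2.73 for discharge and 2.72 for recovery, and shifts of 0.3 gave 3.12 and 3.07. The hazard ratios are not settled either: the simulation in SAP Section 6 uses 1.7 for discharge and 1.35 for recovery. With those values the truly adverse ±1 cell gives mean Z 3.49 (95% above 1.96) for discharge and 0.42 (8%) for recovery. So the sizes are illustrations, but the direction does not depend on them.

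Finally, the documents do not show whether the formula or the sentence is the slip. The sentence's orientation, larger is worse, matches Section 9.2.1.3. That is fair, and either correction is acceptable if it is labelled.

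**Conclusion.** The concern holds. The formula in SAP Section 9.1.1.3 and the sentence interpreting it contradict each other, for both primary endpoints and under any baseline hazard, and nothing else in either document resolves it.

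The harm is conditional: it arises if the program follows one statement and the grid or labels follow the other. In that case, at hazard ratios of 1.45 and 1.7 with illustrative shifts of ±1, the cell presented as worst for SNG001 would exceed 1.96 in every simulated trial, while the true one would do so in only about half. The primary Cox analyses, the Hochberg test and the jump-to-reference imputation (γ = 0) are not touched. It should be corrected before the analysis is programmed or reported, but it does not threaten the primary inference.

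**What to change.** - Make formula and text agree. The simplest way is to keep the formula and swap the two statements: γ > 0 earlier, γ < 0 later. γ then has the same sign convention as β, and exp(γ) reads as a hazard ratio. If the exponent is changed to +γ instead, the multiplier becomes exp(−γ) and must be labelled so.
- Label the heat-map axes and the table with the multiplier of the discharge or recovery hazard after withdrawal, noting that values below 1 mean later events. If the formula is kept, add a sentence that this orientation is opposite to that of the parameter in Section 9.2.1.3.
- State the γ grid, with both signs in each arm, and give the imputed proportion discharged or recovered for each γ, so that a reversal would show.
- Check that the program matches.
- As a clarification only, say that imputed times beyond Day 28 are censored at Day 28. Table 8 already implies this for withdrawals, whose time is "right censored at the time of withdrawal from the study or at 28 days, whichever occurs first".

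The cost is two or three sentences in Section 9.1.1.3 and a check of the code and axis labels. No new data are needed.

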#### 9.1.1.4 *Supportive Estimands*

A supportive estimand of the primary endpoint will estimate the hazard ratio of SNG001 versus placebo for the time to hospital discharge of patients in the per protocol population. Reasons for excluding patients from the PP population are described in [Section 7.1.2](#). Of note, many of the reasons are based on assessments prior to randomisation and treatment and so the exclusions are independent of treatment. Intercurrent events will be handled as per table 9.

**Table 9: Intercurrent events and policies for the supportive estimand of time to hospital discharge**

Intercurrent event	Policy
Death	Composite variable: Patients who die during the study period will have time to hospital discharge right censored at 28 days (the maximum time to discharge).
Missed 2 of the first 3 scheduled doses	Hypothetical (estimand for a situation with treatment compliance): The time to hospital discharge will be considered missing if two or more doses of the randomised treatment were missed within the first three days of therapy, with the corresponding patients excluded from the PP analysis set. A single dose within the first three scheduled dosing days is not expected to be sufficient for the study drug to be effective, therefore this approach will help establish the true treatment effect. It is assumed that such exclusions are not related to treatment.
Other premature treatment discontinuation and missed doses	Treatment policy: The time to hospital discharge will be used regardless of treatment discontinuation and the number of missed doses (other than missing 2 out of the first 3 scheduled doses).
Withdrawal from study following hospital discharge	Hypothetical: The time to hospital discharge will be used regardless of study withdrawal where discharge was sustained for 7 days. Otherwise patients will be censored at the last date known to be hospitalised for patients who withdrew during the 7 day rebound period. This approach has been proposed because discontinuation during the rebound period is expected to be due to lack of interest/lack of motivation/lack of time to continue participating in the study rather than relapse.
Withdrawal from study prior to hospital discharge	While-on-study: Time to hospital discharge will be right censored at the time of withdrawal from the study or at 28 days, whichever occurs first. The evaluation period for this endpoint is 28 days, therefore estimating the time to hospital

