4.5 Dosage and Administration

While hospitalised, all patients will take their doses of study medication under the supervision of study staff. During administration of study medication, study sites should ensure they adhere to any local requirements and guidelines for performing inhalation in patients with COVID-19.

SNG001 nebuliser solution is presented in glass syringes containing CCI mL of drug product solution containing CCI MIU/mL of IFN- β 1a. The CCI device should be filled with the contents of two syringes (if randomised to Arm 1).

The placebo nebuliser solution is presented in glass syringes containing CCI mL of solution containing only the excipients of the SNG001 solution. The CCI device should be filled with the contents of two syringes (if randomised to Arm 2) (See Appendix A).

If a patient requires supplemental oxygen during inhalation of the study medication, a nasal cannula can be used. Oxygen flow rate via a nasal cannula during study medication administration should not exceed CCI L/minute.

If oxygen supplementation using a nasal cannula during study medication administration is insufficient to ensure adequate oxygen saturation, additional oxygen can be provided by using both a nasal cannula and the oxygen port located on the bottom of the CCI CCI chamber. With this mode of oxygen supplementation, the oxygen flow rate via a nasal cannula should not exceed CCI L/minute and the flow rate to the CCI chamber should not exceed CCI L/minute.

Administration of study medication to patients receiving high-flow nasal oxygen therapy is not permitted as it is likely to result in suboptimal doses being delivered. However, patients receiving high-flow nasal oxygen therapy may, during administration of study medication, receive oxygen via a low-flow nasal cannula or **CCI** **CCI** chamber, as described above, if clinically tolerated.

Patients will inhale study medication once a day for 14 days. Administration of study medication should be carried out in compliance with any applicable local regulations for inhalation in COVID-19 patients.

The study medication should be removed from the fridge for a minimum of 15 minutes prior to taking the dose and for no longer than two hours.

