#### 7.1.2 Per Protocol Population

The Per Protocol (PP) analysis population will include all patients within the ITT population who do not have any protocol deviations with an impact on efficacy on or prior to Day 35 and will be used for supportive analyses of efficacy endpoints, as appropriate. Relevant protocol deviations may include, but are not limited to the following:

- Patient was not admitted to hospital due to the severity of their COVID-19.
- Patient did not have a positive RT-PCR virus test by RT-PCR at screening. Evidence of ongoing SARS-CoV-2 infection for more than 3 weeks, confirmed by a validated molecular assay or validated antigen assay.
- OSCi score at baseline was  $\neq 4$ .
- Patient is receiving mechanical ventilation or is in intensive care prior to randomisation.
- Patient could not use a nebuliser with a mouthpiece at baseline.
- Patient failed to receive at least two full doses of the scheduled doses in the first 3 days after randomisation.
- No post baseline OSCi assessments were performed.
- Patient was not discharged from hospital for reasons other than the severity of their condition.

Blinded protocol deviation data will be reviewed routinely in accordance with the protocol deviation plan. Decisions regarding the exclusion of patients from the PP population who have completed the day 35 assessments or who have withdrawn from the study and have all data available and no outstanding data queries will be made during these meetings. Following completion of the study database the status of all patients with regards to the PP population will be reviewed and confirmed.

Following study unblinding, the randomisation schedule will be used to confirm if the randomised drug was correctly administered at each assessment by comparing the syringe numbers entered into the database against the syringe numbers in the material lists. Patients randomised to SNG001 will be excluded from the PP population if SNG001 was administered on less than 2 occasions in the first 3 days of treatment (either missed doses or incorrectly treated with placebo). For patients randomised to Placebo,

assessments of OSCi, BCSS, NEWS2 and EQ-5D-5L conducted on or after the first dose of SNG001 will be excluded from analyses of the PP population.

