### 8.6 Treatment Compliance

Percentage treatment compliance will be summarised for the Safety population.

Treatment compliance is calculated as total number of received doses/ total number of scheduled doses x 100, where the total number of scheduled doses only includes doses prior to study withdrawal.

Percentage treatment compliance will be summarised through descriptive statistics and the number and percentage of patients with < 80%, 80% - <100% and 100% compliance will be presented.

Treatment compliance will also be summarised as the number and percentage of patients that missed dose due to:

- OSCI score of 5 or above
- Other reasons

The number of patients who received partially administered doses will also be summarised alongside the reason for partial administration.

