## Statistical Analysis Plan (RotW)

Final v1.0, 08FEB2022

SG018

	approach will help establish the true treatment effect. It is assumed that such exclusions are not related to treatment.
Other premature treatment discontinuation and missed doses	Treatment policy: Severe disease will be determined regardless of treatment discontinuation and the number of missed doses (other than missing 2 out of the first 3 scheduled doses).
Withdrawal from study	While-on-study: Patients will only be considered having severe disease if observed and recorded whilst participating in the study. This assumes the treatment effect is independent to reason for study withdrawal.
Other protocol deviations affecting efficacy	Hypothetical (estimand for a situation with no protocol deviations affecting efficacy): To establish the true treatment effect all OSCI assessments will be considered missing if protocol deviations affecting efficacy are recorded on or prior to Day 35.
Medications affecting efficacy	Treatment policy: Severe disease will be determined regardless of any concomitant medication use.

A second supportive estimand will estimate the difference in probabilities for SNG001 versus placebo for progression to severe disease or death within 35 days of first dose in the per protocol population who do not receive medications affecting efficacy. Medications affecting efficacy will be defined as COVID-19 therapies which are approved for use (including emergency use) at the time of the primary analysis and will be handled as per table 16.

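### The per-protocol rule on early missed doses can drop patients because they progressed or died, while the SAP assumes such exclusions are unrelated to treatment

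*SAP*

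**What the plan says.** SAP 7.1.2 lists this among the deviations that can remove a patient from the per-protocol set: "Patient failed to receive at least two full doses of the scheduled doses in the first 3 days after randomisation". A check after unblinding repeats the rule for the active arm: "Patients randomised to SNG001 will be excluded from the PP population if SNG001 was administered on less than 2 occasions" in the first three days, and it counts missed doses as well as wrong treatment.

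The supportive estimands carry the same rule. In Table 9 the discharge time of a patient who missed two or more of the first three doses is treated as missing, "with the corresponding patients excluded from the PP analysis set", followed by "It is assumed that such exclusions are not related to treatment". Table 15, for progression to severe disease or death, ends its row the same way: "approach will help establish the true treatment effect. It is assumed that such exclusions are not related to treatment". The row recurs in Tables 10, 12, 13, 16, 18, 19, 21 and 22. Protocol 8.4 contains the missed-dose rule, but not the statement that it is unrelated to treatment.

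SAP 8.6 has a descriptive summary of why doses were missed: "Treatment compliance will also be summarised as the number and percentage of patients that missed dose due to" one of two causes, "OSCI score of 5 or above" or anything else. Protocol 4.5 states: "Administration of study medication to patients receiving high-flow nasal oxygen therapy is not permitted". Its next sentence lets such patients be dosed if they tolerate lower-flow oxygen for the duration of the dose. Footnote 8 of the study schedule gives ventilation as its example of why a patient stops dosing.

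**The concern.** An OSCI score of 5 or above is both a reason for a missed dose and, under SAP 5.3.1.3, an event in the first key secondary endpoint. A patient who is dosed on Day 1 and progresses or dies before the Day 2 dose may receive nothing on Days 2 and 3 for that reason. The rule then removes the patient from the per-protocol analysis of progression, intubation or death on account of the event being analysed.

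That is selection on the outcome after randomisation. The SAP presents these analyses as helping to establish the true treatment effect. If early failures differ between arms, the supportive result shifts in a direction that the reader cannot recover from it.

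**Working it through.** The plan gives no figure on this point, so the check is first textual and then illustrative.

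**Can the event cause the exclusion?**

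1. OSCI 5 or above is a listed cause of a missed dose (SAP 8.6), through the restriction in protocol 4.5 and the example in schedule footnote 8. Schedule footnote 2 places assessments before the dose, so a score of 5 recorded on Day 2 precedes that day's dose.
2. SAP 7.1.2 makes no exception for doses missed through deterioration or death.
3. SAP 9.1.1.4 and its sister sections defend the per-protocol exclusions by noting that many rest on information from before randomisation. This one does not.
4. The tipping-point and jump-to-reference analyses (SAP 9.1.1.3 and 9.2.1.3) deal with withdrawal from the study, not with this exclusion.
5. For an early death, Tables 9 and 15 have a Death row that keeps the patient and a missed-dose row that can remove the same patient. Neither is given precedence. Tables 21 and 22 have no Death row.

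So the path from event to exclusion exists, and nothing in the SAP closes it.

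**How much could it matter?**

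Inputs:
- Arm size: 305 (SAP Section 6).
- Assumed, not in the documents: severe disease or death p0 = 20% on placebo and p1 = 14% on SNG001.
- Assumed, not in the documents: a fraction q of each arm, 2% or 4%, progresses or dies early enough to be excluded. That is 0.02 × 305 = 6.1 or 0.04 × 305 = 12.2 patients.

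Every excluded patient is an event, so:
- per-protocol risk = (p − q)/(1 − q)
- per-protocol odds = (p − q)/(1 − p)

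With nobody removed, the odds ratio is (0.14/0.86)/(0.20/0.80) = 0.65 and the difference is 6.0 points.

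| Removed, placebo / SNG001 | Risk, placebo | Risk, SNG001 | Difference (points) | Odds ratio |
|---|---|---|---|---|
| 4% / 2% | 0.16/0.96 = 16.7% | 0.12/0.98 = 12.2% | 4.4 | (0.12/0.86)/(0.16/0.80) = 0.70 |
| 2% / 4% | 0.18/0.98 = 18.4% | 0.10/0.96 = 10.4% | 8.0 | (0.10/0.86)/(0.18/0.80) = 0.52 |
| 2% / 2% | 18.4% | 12.2% | 6.1 | (0.12/0.86)/(0.18/0.80) = 0.62 |
| 4% / 4% | 16.7% | 10.4% | 6.3 | (0.10/0.86)/(0.16/0.80) = 0.58 |

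With no true effect (20% in both arms), balanced removal leaves the odds ratio at 1.00. Removing 4%/2% gives 0.18/0.16 = 1.13, and 2%/4% gives 0.16/0.18 = 0.89.

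For time to discharge, a large simulation (400,000 patients) used exponential times, 70% of placebo patients discharged by Day 28 (protocol 8.1) and no dropout. It drew all excluded patients from those not discharged by Day 28. A true hazard ratio of 1.45 became about 1.47 to 1.49 with balanced removal, 1.41 with 4%/2% and 1.54 with 2%/4%. A true ratio of 1.0 became about 1.00, 0.97 and 1.04 respectively.

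**The case against.** The strongest reply is that nothing decisive depends on these analyses. The ITT primary and key secondary estimands use a treatment policy for missed doses (Tables 8, 11, 14, 17 and 20), and SAP 7.6 confines formal testing to the primary and key secondary endpoints. That stands. A reader might infer that early benefit or harm vanishes from the trial's results. It does not, because those events remain in every ITT analysis.

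Second, an exclusion related to outcome is not thereby related to treatment. The SAP does not expect one dose in the first three days to work, and an excluded patient has had at most one, so exclusions may be balanced. That is a fair argument, and the documents show no imbalance. But balance is only assumed, intolerable adverse events are a listed reason to stop study medication (protocol 4.3.1), and balanced removal still moves the odds ratio when there is a true effect.

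Third, a reader might infer that all early progressors are lost. They are not. Some patients on high-flow oxygen may still be dosed under protocol 4.5, and a patient dosed on Days 1 and 2 who progresses on Day 3 stays in. SAP 8.6 covers the whole treatment period and says nothing about how often this happens early.

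Fourth, the SAP already reports the size of the per-protocol set (8.1), reasons for missed doses (8.6) and the number meeting the early-dose criterion (8.7), by treatment. This would reveal a gross imbalance. No table, however, crosses the reason with the first three doses.

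**Conclusion.** The point holds for the supportive per-protocol analyses and for nothing beyond them. The rule allows a patient to be removed because of the endpoint event, and the SAP's assumption that such exclusions are unrelated to treatment is untested and sits badly with its own list of reasons for missed doses. For early deaths the supported statement is narrower: two table rows conflict and no precedence is given. It would go too far to say that every such death is excluded.

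Under the assumed 20% v 14% event rates and 2% to 4% removal per arm, the odds ratio for severe disease or death moves from 0.65 to somewhere between 0.52 and 0.70, and the difference from 6 to between about 4.4 and 8 points. The direction depends on which arm loses more early failures; if SNG001 loses more, the drug looks better than it is. These figures illustrate and do not estimate, since the documents give no early-progression rates. The discharge figures also take every excluded patient to be undischarged at Day 28.

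**What to change.** In SAP 7.1.2 and Tables 9, 10, 12, 13, 15, 16, 18, 19, 21 and 22:

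- Do not count as missed, for this rule, any of the first three doses not given because of death or OSCI 5 or above. Keep those patients in the per-protocol set with their observed outcome.
- State that the Death row takes precedence over the missed-dose row. In Tables 21 and 22, which have no Death row, state that a death counts whatever the number of doses received.
- Replace the sentence assuming no relation to treatment with a table of early-dose exclusions by arm and reason, with adverse events shown separately.
- Record the departure from protocol 8.4 in SAP Section 15.

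This changes which patients are analysed, not how anyone is dosed. No new data are needed, since protocol 4.6.3 already requires the reason for each missed dose in the eCRF. The cost is that a few patients with little exposure stay in a supportive set, which dilutes the compliance estimand slightly. Early misses for adverse events or other reasons would still lead to exclusion; keeping those patients too would cut further into that estimand, and the new table lets a reader judge whether they matter.
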